### Funding Source

Type	Number/Code	Name/Title
Sponsor	053500	IVOCLAR NORTH AMERICA, INC.
Institutional Proposal	00346994	CLINICAL EVALUATION OF A UNIVERSAL ADHESIVE IN NONCARIOUS CERVICAL LESIONS
Award	064329-00001A	CLINICAL EVALUATION OF A UNIVERSAL ADHESIVE IN NONCARIOUS CERVICAL LESIONS
Award	064329-00002B	CLINICAL EVALUATION OF A UNIVERSAL ADHESIVE IN NONCARIOUS CERVICAL LESIONS

### Subjects

Subject	Count
Total	33

**Areas of Research**

Code	Description
000001	All Research Areas

### Amendment/

### Renewal

Type	Version	Status	Created Date	Summary
Amendment	004	Submitted to IRB	02/16/2015	amendment 4 - remove saliva inclusion criteria

### Amendment/Renewal Summary

Summary	Editable Modules
amendment 4 - remove saliva inclusion criteria	Add / Modify Attachments and Notes,

KC IRB

Protocol #: 1403626552A004

Investigator: [name]

Summary Printed 02/17/2015

---

## Appendix G-3

Indiana University School of Dentistry  
 Graduate Student Research Proposal Abstract Form  
 (for review by the IUSD Research Subcommittee)

Project Title: Clinical Evaluation of a Universal Adhesive in Non-Carious Cervical Lesions

Name

Signature\*\*

Principal Investigator:	[name]	
Co-investigator (student):	[name]	
Research Committee:	[name]	
	[name]	
	[name]	
	[name]	

Project Biometrist: [name]

Department/Program: Operative / Preventive

Cost of Project: \$40,532 Dates of Project: Feb 2014 - May 2016

Use of: Human Subjects or Tissues: ✓ Animals: \_\_\_\_\_ Biohazards or rDNA: \_\_\_\_\_

Reviewed by [name] (IRB, only if human subjects involved) ✓

Reviewed by [name] (Good Clinical Practice, only if human subjects involved) \_\_\_\_\_

Reviewed by [name] (Research Billing Compliance, only if human subjects involved) \_\_\_\_\_

\*\*Signature indicates that the proposal has been read and approved.

Place Abstract on separate page and attach prior to remainder of proposal.

Clinical Evaluation of a Universal Adhesive in Non-Carious Cervical Lesions

Background/Relevance: For decades, resin adhesives have been used to restore non-carious cervical lesions for esthetics and/or patient comfort. New “universal adhesives” claim to simplify the process of bonding resin composites to tooth structure while maintaining or exceeding the quality of previous adhesive systems. Since dentin and enamel substrates are vastly different with respect to composition and therefore require different bonding protocols, some have advocated a “selective etch” procedure in which the enamel and dentin are etched differently but may still be bonded using a similar bonding agent. The purpose of this study is to determine whether or not a selective etch protocol used with a universal adhesive provides significantly improved results in comparison to a self-etch protocol when restoring non-carious cervical lesions.

Rationale: In vitro studies have shown statistically significantly superior marginal adaptation and color stability with a selective etch technique, but there are currently no prospective in vivo studies greater than 6 months comparing the efficacy of selective vs. self- etch techniques in conjunction with a universal adhesive.

Methods: Thirty-three patients with at least two non-carious cervical lesions (NCCLs) will receive one restoration utilizing the self-etch universal adhesive (Adhese Universal, Ivoclar Vivadent) with no separate enamel etching and another restoration utilizing the universal adhesive and a selective etch protocol in which enamel is etched with 37% phosphoric acid. The adhesive and Tetric composite will be provided by Ivoclar and manufacturer’s instructions will be followed for placement of the restorations.

Alternate Hypothesis: Selective-etch restorations will show superior retention rates, marginal adaptation, and color stability after 2 years compared to self-etch restorations.

Relevance: With so many different types of resin adhesives and numerous proposed methods, this study could provide evidence supporting one protocol and eliminate some of the confusion associated with resin bonding protocols.

## Clinical Evaluation of a Universal Adhesive in Non-Carious Cervical Lesions

### **Background:**

Non-carious cervical lesions (NCCLs) have been well documented in the dental literature for over a century. Differing opinions exist concerning the etiology of NCCLs, but many agree that the etiologies differ and include abrasion, erosion, attrition, and abfraction, a term coined in 1991. Although a few patients may not experience adverse effects from the presence of NCCLs, many patients experience sensitivity ranging from mild to severe. The esthetics of the dentition may also be compromised by the presence of NCCLs. For decades, resin adhesives have been used to restore non-carious cervical lesions for esthetics and/or patient comfort; restoration of these lesions with a bonded resin restoration has been shown to be more effective than no treatment or topical treatment with a desensitizing dentifrice. Since the advent of “fourth generation” (also referred to as “3-bottle”) resin bonding agents in the 1990s, the primary focus in the development of resin adhesives has been simplifying the components and thus the protocol for placing resin composite restorations. New “universal adhesives” claim to simplify the process of bonding resin composites to tooth structure while maintaining or exceeding the quality of previous adhesive systems. Since dentin and enamel substrates are vastly different with respect to their composition and therefore require different bonding protocols, some have advocated a “selective etch” procedure in which the enamel and dentin are etched differently but may still be bonded using the same bonding agent. An *in vitro* study by Hanbusa et al (2012) indicated that use of a universal adhesive with selective etching of enamel with phosphoric acid provides better bonding efficacy than when the adhesive is used as a

self-etch alone. An *in vivo* study performed by Mena-Serrano et al (2012, 2013) has also shown similar results, but since significant hydrolysis of the dentin-resin interface continues to occur after six months or even twelve months, a longer clinical trial is indicated which more accurately depicts longer term clinical success. Conversely, a 3-year study was previously conducted by Can Say, et al (2013) to compare self-etch and selective-etch techniques, but with a two-step bonding system instead of a one-step system^10.

### **Purpose/Specific Aims:**

The purpose of this prospective clinical trial will be to evaluate the efficacy of a newly formulated “universal” dental adhesive formulation in adult noncarious cervical lesions using self-etch and selective etch approaches; the aim is to determine whether or not selective etching provides significantly improved retention and/or better resistance to enamel margin discoloration in comparison to self-etching over a 24 month period.

### **Hypothesis:**

The alternate hypothesis is that the restorations placed utilizing a selective etch method will yield superior retention, marginal adaptation, and less marginal discoloration than restorations placed with the self-etch method.

The null hypothesis is that there will be no significant differences with respect to retention, marginal adaptation, or marginal discoloration when comparing restorations placed with selective etch and self-etch methods.

## **Materials and Methods**

### **1.0 Inclusion/Exclusion Criteria**

A total of 33 patients ranging in age from 20 to 75 years of age will be recruited for this study. Roughly 10 patients will be in the following age groups: 20-39, 40-59, and  $\geq 60$ .

The study population will be targeted to be comparable in terms of the ratio of men to women. Subjects will be selected that meet the following criteria:

1.1. Inclusion criteria

1. Willing to provide written consent and authorization for participation.
2. Be between 20 and 75 years of age at the time of recruitment
3. Have at least two non-carious cervical lesions present in canine or premolar teeth;
4. Anticipates availability for recalls (roughly 6 month, 12 month, and 24 month) through the two-year study period
5. The lesions selected will be at least 1 mm in depth (measured with a perio probe) and contain both enamel and dentin margins.

1.2. Exclusion criteria

1. Severe medical complications (organ transplants, cancer, immunocompromised, long term antibiotic or steroid therapy);
2. Active caries on study teeth;
3. Bleeding on probing of study teeth;
4. Generalized severe periodontitis;
5. Patient reported symptoms (burning mouth, loss or diminished taste, saliva amount too little, needs liquids to eat dry foods) or clinical signs (erythematous tongue, chelitis, lack of pooled saliva) associated with dry mouth;

6. Patients determined to be at a high risk of caries as determined by a Caries Risk Assessment

**2.0 Enrollment/Randomization**

The clinical design will use each technique (self-etch and selective etch & rinse) in each of thirty-three subjects. Each subject will have at least two teeth selected for inclusion in the study. The first tooth to be treated will be randomly assigned to one of the two treatment groups using a randomization table. The second tooth will be placed in the second group. If a third tooth is included, a randomization table will determine which treatment it receives.

**3.0 Study Procedures**

3.1 Subject Recruitment

Subjects for this investigation will be selected from patients of record at Indiana University School of Dentistry Clinics that meet the inclusion/exclusion criteria. Dental students, dental hygiene students, and faculty will be briefed on the study criteria to assist in identifying potential subjects. When a potential subject is identified who dentally appears to meet the criteria, the student or faculty member will either contact the principal investigator or student investigator to visit the patient chairside in real time or ask the patient if they would be willing to complete an IRB approved recruitment brochure to allow the investigators to contact them by phone later about the study.

[name]

For those expressing interest in the project, the student investigator will complete the IRB approved telephone interview with the potential subject and schedule them for their study screening/restorative appointment, as applicable.

### 3.2 Screening/Restorative Visit

#### 3.2.1. Consenting

The Principal Investigator or Student Investigator will complete the consenting process with the subjects. Potential subjects will attend a screening visit in which they will be given the IRB approved informed consent and authorization for the release of health information for research form. Upon reading the documents, subjects will be asked if they have any questions. The purpose, procedures, risks and benefits of the study will be reviewed with the subject and the subject will again be asked if they have any questions. If the subject feels they would like to participate, they will be asked to sign and date the consent and authorization forms after having his/her questions answered to his/her satisfaction and feeling he/she has had enough time to make a decision about participating. The person who completed the consenting process with the subject will also sign and date the consent. Copies of both documents will be given to the subject.

#### 3.2.2. Study Screening Procedures

[figure not shown]
After informed consent has been obtained, the Principal Investigator or Student Investigator will review the subject's on file medical record to ensure accuracy (Axium files), ask the inclusion/exclusion questions and perform an exam of the mouth. If the

subject qualifies to participate, the teeth involved in the research study will be identified and randomized to product as described under section 4.

### 3.2.3. Restorative Procedures

Prior to the placement of restorations, the following information will be recorded in the format of the table below:

- Evidence of sclerosis (as determined by glossy appearance and glassy feel when examined with explorer; percentage will be visually estimated)
- The lesion morphology (predominantly saucer-shaped or predominantly notch-shaped)
- Evidence and location of occlusal facets
- Pre-operative sensitivity to a blast of air (from approximately 1cm for 1s) using the “0-10 Numeric Pain Scale”

Patient #: xx

Age: xx

	#	Sclerosis	Lesion Morphology	Occlusal Facets	Pre-Op Sensitivity
Self-Etch Tooth					
Selective etch Tooth					
Tooth # ( )					

Legend:	
Sclerosis:	0= no sclerosis 1= <50% sclerotic 2= ≥50% sclerotic
Lesion Morphology	S= saucer shape V= "V" shape
Occlusal Facets	Yes No
Pre-Op Sensitivity	0-10

Intraoral digital photographs will be obtained. Restorative procedures will be performed by a single provider on each tooth following standard of care procedures for a Class V restoration. Any x-rays needed will be taken as standard of care and not specifically for research purposes. All teeth will be cleaned with pumice in a rubber prophy cup prior to treatment. The subject (patient) will read and sign the Indiana University School of Dentistry's consent for treatment. Standard of care treatment will include:

- No mechanical preparation or beveling of the tooth surface will occur for either treatment group.
- Local anesthetic will be offered to each subject and its use guided by the patient response.
- Rubber dam isolation using a 212 clamp will be used for each restoration.

### 3.2.4. Placing of the Etching Materials and Restorative Materials

At the point in the restorative procedure where the etching and restorative material placement occurs, the operator will follow procedures for each tooth as identified by the randomization schedule and as described below:

a. Self-etch placement

The universal adhesive (Adhese Universal; Ivoclar Vivadent) will be applied utilizing the following instructions from the manufacturer:

*Starting with enamel, thoroughly coat the tooth surfaces to be treated with Adhese Universal. The adhesive must be scrubbed into the tooth for at least 20 seconds. This time must not be shortened. Disperse Adhese Universal with oil and moisture free compressed air until a glossy, immobile film layer results. Light-cure Adhese Universal for 10 seconds using a light intensity of  $\geq 500mW/cm^2$*

If the lesion is greater than 2 mm in any dimension, incremental placement of Tetric EvoCeram composite (Ivoclar Vivadent) will occur with the first increment being placed against enamel. Instructions are described below:

*Apply Tetric EvoCeram in increments of max 2mm and adapt with a suitable instrument. Sufficient exposure to light prevents incomplete polymerization. Remove excess material with suitable finishers or fine diamonds after polymerization. Use silicone polishers as well as polishing disks and strips to polish the restoration to a durable high gloss.*

Each increment will be light-cured using the intensity and duration prescribed by the manufacturer; the curing light will be calibrated at the beginning of each clinic session.

Final restorations will be finished and polished with fluted composite finishing burs and flexible abrasive disks, respectively.

b. Selective etching placement

Total Etch (37% phosphoric acid; Ivoclar) will be placed on the enamel margin with no intentional placement on the dentin within the lesion. The adhesive (Adhese Universal) will then be applied as instructed by the manufacturer. Tetric EvoCeram composite will be placed, light-cured, finished, and polished in the same manner as for the self-etch group.

**Materials Table**

Adhese Universal
Solvent: 25.0%
Ethanol (64-17-5*)
Water (7732-18-5*)
Monomer mixture: 67.1%
HEMA (868-77-9*)
Bis-GMA (1565-94-2*)
Decandiol dimethacrylate (6701-13-9*) Methacrylated phosphoric acid ester (85590-00-7*) Methacrylated polyacrylic acid (9003-01-04; 106-91-2*)
Filler: 4.0%
Fumed Silica (7631-86-9*)
Initiators: 3.8%
Ethyl p-Dimethylamino-benzoate (10287-53-3*)
Campherquinone (10373-78-1*)
Dimethylamino ethylmethacrylate (2867-47-2*)
Stabilisers: 0.1%
Butyl hydroxy toluene (128-37-0*)
Hydroquinone monomethylether (150-76-5*)

\* CAS No.

### 3.2.5 Post Procedure Images and Impressions

Post-operative intraoral images will be obtained and impressions made using polyvinyl siloxane and poured in epoxy for future SEM marginal analysis. Each restoration will have a baseline evaluation to document retention, marginal discoloration, and marginal adaptation.

### 3.3. Follow Up Visits

Recall examinations will be conducted by two IUSD faculty members ([name], [name], [name], [name], [name], [name]) at approximately 6, 12, and 24 months from the screening/restorative visit. The subject's medical history will be updated in Axium and the subject will answer questions to assure continued eligibility in the study. Evaluation of sensitivity and modified USPHS criteria to include retention, marginal discoloration, and marginal adaptation will occur and recorded in the table (below). In addition, an overall determination of clinically acceptable or not clinically acceptable will be made at each evaluation visit. Intraoral digital images and impressions will be made at each recall appointment. The subjects will be compensated with checks in the amounts of \$25, \$50, and \$75 at 6,12, and 24-month follow-up visits, respectively. Restorations deemed to be not clinically acceptable within the timeframe of the study will be replaced using normal dental school protocol at no cost to the patient.

Baseline	#	Retention	Marginal Adapt.	Marg. Discoloration	Sensitivity	Clinically Acceptable?
Tooth # (SfE)						
Tooth # (SelE)						
Tooth # ( )						
6 Month Recall	#	Retention	Marginal Adapt.	Marg. Discoloration	Sensitivity	Clinically Acceptable?
Tooth # (SfE)						
Tooth # (SelE)						
Tooth # ( )						

12 Month Recall	#	Retention	Marginal Adapt.	Marg. Discoloration	Sensitivity	Clinically Acceptable?
Tooth # (SfE)						
Tooth # (SelE)						
Tooth # ( )						
24 Month Recall	#	Retention	Marginal Adapt.	Marg. Discoloration	Sensitivity	Clinically Acceptable?
Tooth # (SfE)						
Tooth # (SelE)						
Tooth # ( )						

USPHS Criteria

	A: There is no discoloration between the tooth and the restoration
Marginal Discoloration	B: Discoloration is present without axial penetration
	C: Discoloration is present with axial penetration
	A: Present
Retention	B: Partial loss of restoration
	C: Absent/complete loss of restoration
	A: Excellent continuity at resin–enamel interface; explorer exhibits no catch or one way catch when drawn across margin
Marginal adaptation	B: Explorer exhibits a two-way catch, indicating a crevice, when drawn across margin
	C: Marginal crevice present; exposes base or dentin

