#### **4.0 Statistical Considerations**

The two techniques will be compared for differences in sensitivity, retention, marginal discoloration, marginal adaptation, and clinical acceptability at each follow-up visit using Cochran-Mantel-Haenszel tests for stratified, ordered categorical outcomes. The study subjects are considered the 'strata' in this method so that the comparisons properly account for the use of both techniques in each subject. This method also easily extends to having multiple teeth receiving each technique for each patient.

With a final sample size of 30 subjects, the study will have 80% power to detect a 35% difference between the two treatment methods, assuming two-sided tests of paired proportions and a 5% significance level. To account for attrition the study will enroll 33 subjects.

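### The Section 3.3 rating form prints the bonding technique beside the two main study teeth at every visit, and the available text describes no masking of the evaluators

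*Combined protocol and SAP*

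**What the plan says.** Section 3.3 states that "Recall examinations will be conducted by two IUSD faculty members" at about 6, 12 and 24 months, and that "Evaluation of sensitivity and modified USPHS criteria to include retention, marginal discoloration, and marginal adaptation will occur and recorded in the table (below"). It adds that "an overall determination of clinically acceptable or not clinically acceptable will be made at each evaluation visit".

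The table has four blocks: baseline and the three recalls. In each block the first row is headed `Tooth # (SfE)` and the second `Tooth # (SelE)`. The row for an optional third tooth has an empty bracket. Each row takes retention, marginal adaptation, marginal discoloration, sensitivity and clinical acceptability.

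The Hypothesis section is directional: selective-etch restorations "will yield superior retention, marginal adaptation, and less marginal discoloration than restorations placed with the self-etch method". Section 4.0 states: "The two techniques will be compared for differences in sensitivity, retention, marginal discoloration, marginal adaptation, and clinical acceptability at each follow-up visit". Every outcome on the form therefore feeds a planned comparison.

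The available text does not mention masking or coded tooth labels. It does not require evaluators to be separate from the operator, and it does not say who fills in the form.

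**The concern.** Anyone who rates from this form sees which technique each of the two main teeth received, at the moment of rating and next to the tooth it is compared with. Two of the three outcomes in the directional hypothesis, marginal adaptation and marginal discoloration, are examiner judgements. Clinical acceptability is a global judgement with no stated criteria.

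Because both techniques are used in the same mouth, a tendency to rate one label more harshly becomes a difference between techniques. Randomizing the first tooth and stratifying by subject do not remove it. What is at stake is whether a reported advantage for selective etching reflects the restorations or the label.

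**Working it through.** **1. What the form shows.** Technique is pre-printed on 2 of 3 rows in 4 of 4 blocks. The three recall blocks matter most, because Section 4.0 compares techniques at follow-up visits and plans no baseline comparison.

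**2. Is the label needed there?** No. The pre-operative table in Section 3.2.3 already links technique to tooth number; its rows include "Selective etch Tooth". Tooth number alone is enough to join the two records.

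**3. Could evaluators otherwise be kept unaware?** Probably. Under Section 3.2.4 both groups receive the same adhesive and composite, finished in the same way, and the planned difference is the acid etch on enamel. The documents do not claim that the finished restorations look identical, but they describe no other planned difference that an evaluator would see.

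**4. Which outcomes are exposed?** Complete loss of a restoration leaves little to judge. For marginal adaptation, grade A requires that "explorer exhibits no catch or one way catch when drawn across margin" and grade B requires a two-way catch. That anchor narrows discretion without removing it. Clinical acceptability has no anchor.

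**5. Is there an independent check?** Section 3.2.5 has impressions "poured in epoxy for future SEM marginal analysis", but Section 4.0 plans no analysis or masked reading of them.

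**6. How much could a label-linked shift matter?** The plan gives no figure for rating bias, so there is none to reproduce. The following is an illustration.

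- From Section 4.0: n = 30 subjects, two-sided 5% test, paired proportions.
- Assumed: ratings collapsed to A versus B/C; true B/C rate b, equal in both groups; teeth independent within subject; a shift s that raises the recorded self-etch rate to b + s.
- Discordant-pair probabilities: p10 = (b + s)(1 − b), where only self-etch is rated B/C, and p01 = b(1 − b − s), where only selective etch is.
- Rejection rate: the number of discordant pairs m is Binomial(30, p10 + p01). Given m, the number x against self-etch is Binomial(m, p10/(p10 + p01)). The uncorrected McNemar test, to which the planned Cochran-Mantel-Haenszel test reduces for 1:1 binary pairs, rejects when (2x − m)²/m > 1.96². Probabilities are summed over all m and x.

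Worked inputs for b = 0.20:

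- s = 0: p10 = p01 = 0.20 × 0.80 = 0.16.
- s = 0.05: p10 = 0.25 × 0.80 = 0.20 and p01 = 0.20 × 0.75 = 0.15.
- s = 0.10: p10 = 0.30 × 0.80 = 0.24 and p01 = 0.20 × 0.70 = 0.14.

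False-positive rates:

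| True B/C rate | Test | No shift | 5 points | 10 points |
|---|---|---|---|---|
| 10% | Uncorrected | 4.8% | 8.1% | 16.8% |
| 10% | Exact | 1.0% | 3.2% | 9.6% |
| 20% | Uncorrected | 4.3% | 6.4% | 12.6% |
| 20% | Exact | 2.2% | 3.7% | 8.3% |
| 30% | Uncorrected | 4.4% | 6.3% | 11.7% |
| 30% | Exact | 2.5% | 3.8% | 7.8% |

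The shifts amount to 30 × 0.05 = 1.5 and 30 × 0.10 = 3 re-rated self-etch teeth. Keeping the ordered scores A = 0, B = 1, C = 2, with assumed frequencies of 80/15/5% and re-rating from A to B, the statistic Σd/√Σd² (d = self-etch minus selective-etch score) gives 4.7%, 6.3% and 10.9%. This version is closer to the planned ordered test.

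**The case against.** The strongest reply is that the table in Section 3.3 may be only a layout. Sections 5.4 and 5.4.1 refer to case report forms supplied by the investigator, which are not in the documents. The budget lists evaluators and an assistant, so someone else may hold the form. The plan never claims masking, so this is an omission rather than a contradiction, and some pages were removed before review. These points stand as limits: the documents do not show that evaluators were unmasked. They do not remove the problem, because Section 3.3 says the ratings go into that table, and nothing available provides for a recorder who withholds the label.

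A second reply is that two examiners and the USPHS anchors restrain bias. They do in part, but two examiners reading the same label share the same cue.

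A third is that the Purpose/Specific Aims section names only retention and enamel margin discoloration, and retention is hard to misjudge. That is fair. It still leaves one of the two named aims exposed, as well as marginal adaptation in the hypothesis and clinical acceptability in Section 4.0.

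A fourth is that the shifts are invented. They are. With the exact test a 5-point shift stays below 5% at every base rate tried, and 10 points is under a third of the 35% difference the trial is powered for. The conclusion therefore does not rest on the table of rates.

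**Conclusion.** The concern holds. Followed as written, the plan places the technique beside examiner-judged outcomes in a directional within-mouth comparison, and the available text contains no safeguard. The finding is that masking is unprotected, not that bias occurred. The label count and the absence of masking text come directly from the documents. The amount of bias cannot be derived from them. Under the stated assumptions (true B/C rates of 10% to 30%, independent teeth), a 5-point shift gives false-positive rates of about 6% to 8% uncorrected or 3% to 4% exact. A 10-point shift gives about 12% to 17% or 8% to 10%. The point should be fixed because the cue is avoidable and the remedy cheap.

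**What to change.** Head every baseline and recall row, including the third tooth, with the tooth number only, in ascending order. Add to Section 3.3:

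> The technique key stays on the Section 3.2.3 restorative form, stored apart from the recall form. It is withheld from the recall evaluators until their 24-month ratings are complete, and is available to the statistician for the comparisons at each visit. Evaluators are not told the technique and, chosen from the faculty already named, did not place the restorations they rate.

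Two small extensions are worth making: apply the same rule to whoever does the baseline evaluation, and keep any technique entry in the Axium record, which is updated at each recall, out of the evaluators' view. As an optional, best-effort step, do not tell subjects which tooth received which technique.

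The cost is one relabelled form and a few sentences, with no extra visits, measurements or staff. The downside is that the key must be stored separately. This version belongs to Amendment 4, created 02/16/2015, in a project dated February 2014 to May 2016, so some visits may already be on the labelled form. Those cannot be masked afterwards; report which they are and treat their ratings as unmasked.

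### The aim concerns discoloration at the enamel margin, but the form takes one discoloration grade per tooth without location, so the planned data do not isolate the enamel comparison

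*Combined protocol and SAP*

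**What the plan says.** The Purpose/Specific Aims section names two outcomes: retention and "better resistance to enamel margin discoloration in comparison to self-etching over a 24 month period". The Hypothesis section is broader. Its null is that "there will be no significant differences with respect to retention, marginal adaptation, or marginal discoloration" will be found, with no margin named.

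Section 1.1 requires that lesions "contain both enamel and dentin margins". Under section 3.2.4 b, the phosphoric acid "will be placed on the enamel margin with no intentional placement on the dentin within the lesion".

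Section 3.2.5 states: "Each restoration will have a baseline evaluation to document retention, marginal discoloration, and marginal adaptation". The form in section 3.3 has one discoloration column, with one row per tooth at baseline and at 6, 12 and 24 months. Grade A is "A: There is no discoloration between the tooth and the restoration"; grades B and C are separated by axial penetration. None of the three mentions enamel or dentin. In the same table, grade A for marginal adaptation does name a location: "Excellent continuity at resin–enamel interface".

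Section 4.0 tests marginal discoloration undivided, at each follow-up visit, with a Cochran-Mantel-Haenszel test stratified by subject.

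**The concern.** A grade of B or C can come from either margin, and the form does not say which. Read over the whole margin, which is the most natural reading of grade A, the grade mixes the margin where the techniques differ by intent with one where they do not.

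- **Dentin staining similar in both groups.** It dilutes any enamel difference, and a null result is harder still to read as absence of an enamel benefit.
- **Dentin staining different by technique.** Section 3.2.4 b excludes only intentional etching of dentin. The single grade would then combine two effects and could overstate or understate the enamel difference.

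A single chairside grade cannot be split afterwards. Retention, the other outcome in the aim, is not affected.

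**Working it through.** **1. The documents side by side**

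| Place | What is compared or recorded | Margin named? |
|---|---|---|
| Purpose/Specific Aims | discoloration | enamel |
| Hypothesis | discoloration | no |
| 1.1 | lesions eligible for study | enamel and dentin, both required |
| 3.2.4 b | where the techniques differ by intent | enamel |
| 3.2.5 and 3.3 | one discoloration grade per tooth per visit | no |
| 3.3, adaptation grade A | marginal adaptation | enamel |
| 4.0 | discoloration | no |

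This comparison settles the point; the arithmetic below only shows how much it could matter.

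**2. The plan's own power figure**

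Section 4.0 gives 80% power for a 35% difference with 30 subjects, using two-sided paired tests at 5%. For the McNemar test, with difference d and discordant proportion ψ, power = Φ[(d√n − 1.96√ψ) / √(ψ − d²)]. The documents do not give ψ. With d = 0.35, n = 30 and ψ = 0.50: (1.917 − 1.386)/0.614 = 0.864, so power is 80.6%. The stated 80% is attainable and is not disputed. Section 4.0 does not tie the 35% to discoloration.

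**3. Dilution with equal dentin staining (all inputs assumed)**

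Let p be the enamel staining rate and q the dentin staining rate in both groups. A tooth counts as stained if either margin is. If the two margins are independent within a tooth, the whole-margin difference is

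(1 − p_sel)(1 − q) − (1 − p_self)(1 − q) = (1 − q)(p_self − p_sel).

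For a 35-point enamel difference, q = 20% gives 0.80 × 35 = 28 points.

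Power was simulated with 40,000 trials of 30 pairs and the uncorrected two-sided McNemar test at 5%. With a yes/no grade and one tooth per technique, that equals the subject-stratified Cochran-Mantel-Haenszel test. Enamel rates (self-etch/selective) were 52.5/17.5, 45/10 and 65/30%, with latent enamel correlation 0.2 between a subject's teeth. Ranges run over the three rate pairs.

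| q | Difference (points) | Power, dentin staining independent between teeth | Power, dentin staining fully shared |
|---|---|---|---|
| 0 | 35 | 82–90% | 82–90% |
| 5% | 33.25 | 77–82% | 79–88% |
| 10% | 31.5 | 72–74% | 77–87% |
| 20% | 28 | 59–61% | 71–81% |
| 30% | 24.5 | 47–51% | 64–75% |

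Letting the latent correlation between enamel and dentin staining within a tooth run from 0 to 0.7 widens the independent column at q = 20% to 51–67% and at q = 30% to 31–53%. The shared column stays at about 71–81% at q = 20%. At correlations of 0.5–0.7 the difference at q = 20% is about 25–30 points.

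**4. Unequal dentin staining (margins independent within a tooth)**

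The difference is (1 − p_sel)(1 − q_sel) − (1 − p_self)(1 − q_self). For the 45/10 pair:

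- q_self 25%, q_sel 15%: 0.90 × 0.85 − 0.55 × 0.75 = 35.3 points.
- q_self 15%, q_sel 25%: 0.90 × 0.75 − 0.55 × 0.85 = 20.8 points.

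Over the three rate pairs these are 33.3–35.3 and 20.8–22.8 points, against a true enamel difference of 35.

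**The case against.** The best reply is that one sentence is out of line, not the design. The Hypothesis section, sections 3.2.5 and 3.3, and the test in section 4.0 all speak of marginal discoloration without a location, so hypotheses, data and analysis agree. That is correct, and it is why rewording the aim is an acceptable remedy. It does not remove the conflict: the aim, the eligibility rule and the placement of the acid all single out the enamel margin.

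The second reply is that examiners may in practice grade the enamel only, as adaptation grade A suggests, or that location could be recovered later, since "Intraoral digital images and impressions will be made at each recall appointment". Both are possible, but neither is written down. No section limits the discoloration grade to enamel or plans a reading of the images by margin.

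The third reply is that a whole-margin grade still compares the techniques within subjects. If dentin staining is alike in both groups, an observed difference would arise at the enamel, and only sensitivity is lost. This stands under that condition. It also stands that a non-significant enamel-only result from 30 pairs would not prove absence of benefit; separate grading lessens that limit without removing it.

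Finally, every rate in the power illustration is assumed, the grade is reduced to yes/no although section 4.0 plans ordered categories, and the loss is small at 5% dentin staining. All of this is accepted. The illustration shows a range and does not carry the conclusion.

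**Conclusion.** The concern holds. As written, the form and the planned analysis yield no variable that answers the discoloration part of the aim. That follows from the text alone and needs no assumed rate. The consequence runs from slight to substantial, depending on how often dentin margins stain and how that staining is shared between a subject's teeth, neither of which the documents give. The stated 80% power is not itself wrong, and the retention comparison and the broader hypothesis on marginal discoloration are unaffected. This is something the sponsor should change; it does not invalidate the trial.

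**What to change.** In section 3.3, replace the single discoloration grade with an enamel-margin grade and a dentin-margin grade on the same A/B/C scale, at baseline and at each recall. In section 4.0:

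- name the enamel-margin grade as the discoloration outcome for the aim;
- keep the worse of the two grades as the marginal discoloration outcome for the hypothesis;
- report the dentin-margin grade descriptively, without a test.

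The cost is one extra column in each of the four visit blocks, one or two sentences in each of sections 3.3 and 4.0, and slightly longer scoring, with the same visits, evaluators and instruments. The plan now has 5 outcomes × 3 recalls = 15 comparisons. Testing the enamel grade at every recall makes 18; testing it only at 24 months, the horizon in the aim, makes 16. Section 4.0 states no multiplicity adjustment, so the smaller addition is preferable.

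If the sponsor does not intend an enamel-specific conclusion, the alternative is to reword the aim to match the Hypothesis section and to state in section 3.3 that the whole margin is graded. That needs no new data, but it drops the enamel question instead of answering it.
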